5.7 VENUS: DEFINITIONS OF PROCEDURAL SUCCESS OR FAILURE AND INDICATIONS FOR REPEAT PROCEDURES

- 1. Success:** Freedom from AT/AF clinical recurrence on follow-up visits AND less than 30 seconds of AT/AF on a 1 month continuous electrocardiographic monitor .
- 2. Clinical Success.** Freedom from AT/AF clinical recurrence on follow-up visits but documented AF or flutter up to 25% of the time on a 1-month continuous electrocardiographic monitor. The rationale is to account for patients in whom a repeat procedure would not be clinically indicated, yet AF/AT would not be considered cured.
- 3. Repeat procedures. A repeat procedure will constitute an effectiveness failure for the purpose of the primary efficacy endpoint.** However, repeat procedures and their outcomes will be recorded for secondary outcome analysis. First, repeat procedures are a clinical reality in persistent AF, and a single-procedure success endpoint –does not capture it. Second, it is possible that VOM-PV on a first procedure may increase success of a second procedure –e. g. if the recurrences in VOM-PV group are as AT instead of AF. Both represent a clinical failure of the procedure, but a repeat procedure for AT is more likely to succeed.⁶⁵ Repeat procedures will be encouraged to be timed within the first 6 months of the randomization procedure. Although this may seem short, it is our clinical experience that the bulk of AF recurrences tend to occur shortly after the blanking period.¹¹⁵ Thus, we expect a minority of patients to recur late in this window.

Indications for a repeat procedure include:

- Procedure failure: Symptomatic, recurrent persistent AF or flutter detected clinically during the scheduled follow-up visits.
- Less than partial/clinical success: AF or flutter burden on electrocardiographic monitoring exceeding 25% regardless of symptoms. Monitoring will be performed at 6 months post randomization procedure.
- Symptomatic AF or flutter detected on electrocardiographic monitoring regardless of AF or flutter burden. Monitoring will be performed at 6 months post randomization procedure.

Data to be collected during a repeat procedure will include

- a. Documentation of PV isolation: number and location of reconnected PV at the baseline of the repeat procedure.
- b. Perimitral conduction: presence or absence of perimitral block.
- c. Mechanisms of atrial flutter, if present.
- d. Documentation of other RF ablation sites
- e. Documentation of RF time, time to perimitral block (if not already achieved), fluoroscopy time, LA instrumentation time, and procedure time.
- f. Baseline and Final LA voltage map (using any commercially available electroanatomical mapping systems). Measurement of baseline and Final LA scar surface area.

4. Effectiveness (Treatment) Failures

Effectiveness failures towards the primary endpoint will include the following (see Figure 8):

- a. Clinical recurrence of AF or AT after 3-months.
- b. Documented AF or AT of 30 seconds or more on EKG monitor at obtained at 6 and 12 months.
- c. Requirement of a repeat ablation procedure for recurrent AT-AF.
- d. Death.

VENUS and MARS patients who have a recurrence after 3 months post randomization will have a repeat procedure (PVAI). Patients will be deemed to be effectiveness failure for the primary efficacy endpoint of the trial after repeat procedures. Still, subjects will:

- a. Remain in the study for the purpose of all secondary endpoints: these include quality of life, AF burden on event monitoring, success after multiple procedures.
- b. Undergo all clinically necessary procedures and treatments, including prescription of antiarrhythmic therapy and additional procedures needed to control atrial fibrillation or flutter. A crossover VOM procedure will be offered to those randomized to PVAI after 2 in-study procedures.
- c. Data on such additional procedures or treatment will be collected in the Electronic Data Capture system (EDC).
- d. An additional secondary endpoint will be created: total number of procedures performed and requirement of antiarrhythmic drugs.

5. VENUS: Cross-over of patients initially randomized to PVAI only.

If a VENUS patient is originally randomized to conventional PVAI and experiences a treatment failure after a repeat procedure he or she may undergo an additional conventional PVAI ablation procedure during the study. Crossover to VOM ethanol will only be allowed after 2 procedures are performed in the setting of study participation. This is allowed because certain recurrent flutters are particularly suited to respond to VOM ethanol. The primary and secondary endpoints will be computed following their original randomization group.

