5.2 STUDY ENDPOINTS

Primary endpoints:

1. Primary Efficacy Endpoint Freedom from AT/AF clinical recurrence on follow-up visits AND less than 30 seconds of AT/AF on a 1 month continuous electrocardiographic monitor at 6 and 12 months.
2. Primary Safety Endpoint - Acute procedural complications and total mortality.

Secondary Endpoints

1. Freedom from AF/AT after >1 procedure.
2. Freedom from AF/AT on antiarrhythmic drugs.
3. AF burden (% time) on continuous monitoring at 6 and 12 months.
4. Procedural parameters: total procedure, fluoroscopy, total RF ablation time (first procedure), and total extent of ablated LA tissue.
5. Clinical/partial success: less than 25% AF burden on a continuous event monitor at 6 and 12 months from ablation procedure.
6. Sub-acute procedural complications (within 30 days).
7. Recurrence as persistent or paroxysmal AF, or flutter after 1 or 2 procedures.

8. LA function on Doppler echocardiography (LA strain^{114ab}) at 12 months.
9. Incidence and mechanisms of atrial flutters.
10. Cardiovascular hospitalizations and
11. QOL as determined by AFEQT questionnaire.

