1. Freedom from symptomatic AF or flutter AND reduction of AF/flutter to less than 30 seconds in a continuous 4 week monitor at 6 and 12 months	
 12 month continuous ECG page- MARS 12 month continuous ECG page- Venus 	
 6-12 month AF/AT Burden less than 30 seconds on continuous ECG monitoring
2. Safety: Acute procedural complications	
 AE pages Day 7 Telephone FU 	
 Acute AE's related to Day 0 procedure Day 7 reported complications
Secondary Endpoints:		
1. Single vs. 2-procedure success.	
 Status change page 	
 Single: reached primary endpoint #1 after first procedure with no repeats Two procedure: reached primary endpoint #1 after second procedure with no 3rd procedure
2. AF burden (% time) on continuous monitoring at 12 months.	
 6-12 month continuous ECG page- MARS 12 month continuous ECG page- Venus 	
 6- 12 month AF/AT Burden (%) on continuous ECG monitoring
3. Procedural parameters: total procedure, fluoroscopy, total RF ablation time (first procedure), and total extent of ablated LA tissue.	
 PVAI Page VOM page 	
 Total procedure time, PVAI only Total procedure time, VOM procedure Total fluoro time Scar measurements pre and post PVAI and VOM
4. Clinical success: freedom from symptomatic AF/flutter but AF/flutter > 1 min/day < than 1% at 12 months.	
 12 month continuous ECG page- MARS 12 month continuous ECG page- Venus 	
 12 month AF/AT Burden less than 25% continuous event monitor at 6 and 12 months from ablation procedure
5 Sub-acute procedural complications (within 30 days).	
 Symptoms page AE page 	Day 30 reported, procedure related complications via symptoms and/or AEs
6 Recurrence as persistent or paroxysmal AF, or flutter after 1 or 2 procedures.	
 12 lead Ecg page Evaluation for repeat procedure page AE page 	
 Type of recurrence (rhythm) Characterization of recurrence e.g. persistent or paroxysmal for a fib; typical or atypical for a flutter.
7. LA function on Doppler echocardiography (LA strain114ab) at 12 months.	Central echocardiogram page	LA Strain

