	0.15	1.000	1.000	0.977	0.903	0.619
	0.2	0.984	0.939	0.734	0.516	0.369
0.86	0	1.000	1.000	1.000	1.000	1.000
	0.05	1.000	1.000	1.000	1.000	1.000
	0.1	1.000	1.000	1.000	1.000	1.000
	0.15	1.000	1.000	1.000	0.981	0.913
	0.2	1.000	0.986	0.944	0.852	0.619

D) Stopping rules. The trials will be stopped if one of the following occurs:

- Futility/efficacy boundaries reached. As illustrated in Figures S1 and S2, if the upper or lower boundary is reached at the 1/3 or 2/3 data assessment for beneficial efficacy or futility respectively, the trial will be evaluated for early termination.
- Safety. Events will be reported to FDA, NHLBI, and DSMB according to FDA/OHRP requirements and NHLBI adverse event and unanticipated problem reporting policy. Expedited reporting will occur within 7 days of initial receipt of information for fatal or life-threatening unexpected serious reactions and within 15 calendar days for non-fatal, non-life threatening unexpected events. The DSMB will otherwise evaluate overall safety events on a bi-annual basis. An excess of **procedural** adverse events attributable to study procedure will be evaluated for early termination. Procedural adverse events include those that occur within 24 hours of the procedure or those that may be delayed but procedure-related (atrio-esophageal fistula or delayed pericardial effusion). The following are expected to be rare. One event may occur by chance in either treatment groups. Two of the same events in either arm will trigger consideration for study termination after detailed case review:
 - Mortality.
 - Stroke-Transient ischemic attack or systemic embolus.
 - Pericardial effusion requiring drainage

- Raghunathan, T. E., J. M. Lepkowski, J. Van Hoewyk, and P. Solenberger. 2001. A multivariate technique for multiply imputing missing values using a sequence of regression models. *Survey Methodology* 27: 85–95.
- Rubin, D. B. 1987. *Multiple Imputation for Nonresponse in Surveys*. New York: Wiley.
- van Buuren, S. 2007. Multiple imputation of discrete and continuous data by fully conditional specification. *Statistical Methods in Medical Research* 16: 219–242.

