7.0 STUDY ORGANIZATION

7.1 SCHEDULE OF EVENTS

Visit ID	1	2	3	4	5	6	7	8	9
Procedure	screen/ baseline	procedure day 0	prior to discharge	7 days (± 3)	30 day FU (±10) 1mo	90 day FU (±30d) 3mo	180 day FU (±60d) 6mo	9 mo FU (±30d)	360 day FU (±60d) 12 mos.
Informed Consent (prior to study specific procedures)	X								
Eligibility Checklist (PMH, medications, verification of Inclusion and exclusion criteria)	X								
General Medical History & Cardiovascular History with CHADS2-VASC Score)	X								
LAA thrombus exclusion Transesophageal Echocardiogram (within 48 hours) or anticoagulation/LAA exclusion)	X ⁽ⁱ⁾								
Cardiac MRI or CT or Echocardiogram (showing structure & function within 1 year)	X ^(m)								
Randomization	X								
Targeted Physical Exam	X				X	X	X	X	X
12 lead EKG	X	X pre- procedure	X		X	X	X	X	X
Laboratory: CBC, Serum creatinine, and INR – (INR only if patient is taking warfarin ^(g))	X								
AF Quality of Life Questionnaire (AFEQT)	X						X	X	X
Pre-procedure 3D Mapping^(b,j)		X							
VOM Procedure w/ ETOH Injection and Post ethanol map		X ⁽ⁱ⁾							
PVAI Procedure		X							
Post Procedure 3 D Mapping		X ^(c,j)							
Follow-Up Phone Call⁽ⁱ⁾				X					
3-4 Week EKG (Event Monitor)^(d,n)							X		X
Echocardiogram , Central Reader ([name])									X ^(k)
Repeat Procedure allowed^(e)						X	X	X	
AAD Therapy	If appl.	If appl.	If appl.	If appl.	If appl.	Stop AAD ^(a)			
Anticoagulation	X	X	X	X	X	X	X	X	X
Adverse Events	X	X	X	X	X	X	X	X	X

Footnote Key

- (a) Must be in sinus rhythm prior to stopping AAD, may stop if clinically indicated
- (b) Required for both VENUS-AF and MARS-AF groups. For subjects in VENUS-AF, there should be little to no scarring for first procedure. For subjects in MARS-AF group and study patients requiring repeat procedures, maps will assess pre-existing extent of previous ablation lesions and presence or absence of PV reconnection.
- (c) To delineate extent of scar in both PVAI alone and PVAI/VOM groups.
- (d) Continuous 4 week EKG monitoring, will take place at month 6, and 12
- (e) Repeat procedures will be allowed if certain criteria met
- (f) Seven day follow-up phone call to assess post procedure symptoms.
- (g) Baseline INR must be within 24 hours prior to procedure for patients taking warfarin;
- (h) Not applicable.
- (i) For patients randomized to receive VOM ethanol infusion, and who have a vein of Marshall that can be cannulated.

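### Safety is grouped as randomised, with no planned endpoint analysis by ethanol received; if uncannulated patients stay in the VOM-PV arm, the by-arm difference shows about 0.85 of an ethanol-specific excess

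*Combined protocol and SAP*

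**What the plan says.** Section 5.2 makes safety a primary endpoint ("Primary Safety Endpoint - Acute procedural complications and total mortality") and lists a secondary one ("Sub-acute procedural complications (within 30 days").

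The only sentence on grouping closes item 5 of sections 5.7 (VENUS) and 5.8 (MARS): "The primary and secondary endpoints will be computed following their original randomization group". It is written for PVAI patients who cross over, and it makes no exception for safety. Section 7.6 adds that treatment group is the sole identifier carried into the analysis.

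Not everyone in the VOM-PV arm gets ethanol. Footnote (i) of the section 7.1 schedule limits the infusion: "For patients randomized to receive VOM ethanol infusion, and who have a vein of Marshall that can be cannulated". Section 5.5 sets the 1.15:1 allocation to allow for 85% feasibility. Some PVAI patients may get ethanol later: "Crossover to VOM ethanol will only be allowed after 2 procedures are performed in the setting of study participation".

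In the section 6.0 C endpoint table, the safety data fields are "Acute AE's related to Day 0 procedure", complications reported at Day 7, and, for the 30-day endpoint, "Day 30 reported, procedure related complications via symptoms and/or AEs". None is split by cannulation result or by ethanol received, and the pre-specified subgroups do not include such a split.

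**The concern.** Ethanol is the investigational product under the IND. The comparison as randomised is right for the strategy of attempting VOM infusion before PVAI. A reader who wants the event rate among patients who received ethanol is promised no such figure.

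Two things separate the arm from the exposure. VOM-PV patients without ethanol dilute a harm caused by ethanol itself. PVAI patients infused at crossover carry ethanol exposure that no planned endpoint analysis labels as such. At stake is the completeness of the safety report. The efficacy result is not affected.

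**Working it through.** **The plan's feasibility figures.** Section 3.2 reports 89 completed infusions in 106 patients: 89/106 = 84.0%, printed as 85%. The two halves of that series gave 73% and 90%, used here as the range. The arm sizes agree with 1.15:1 (180/156 = 1.154; 37/32 = 1.156).

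**Unexposed patients.** The synopsis gives 180 + 37 = 217 VOM-PV patients over both trials. With f the share infused:

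| f | Infused, 217f | Not infused, 217(1 − f) |
|---|---|---|
| 0.85 | 184.45 | 32.55 |
| 0.73 | 158.4 | 58.6 |
| 0.90 | 195.3 | 21.7 |

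Section 6.0 sizes MARS at 33 per arm. That would give 213 patients and 0.15 × 213 = 32 unexposed, which changes nothing material.

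**Dilution.** Assume uncannulated patients stay in the arm. Let b be the risk without ethanol and e the excess confined to infused patients. Then

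by-arm difference = [f(b + e) + (1 − f)b] − b = f × e.

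At f = 0.85, an excess of 2, 5 or 10 points shows as 1.7, 4.25 or 8.5 points. Over the pilot range the factor is 0.73 to 0.90. It scales the excess and cannot reverse its sign. Harm from attempting cannulation can also occur in failed attempts, so it is diluted less.

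**Effect on reported rates.** Exact (Clopper-Pearson) 95% limits, with any events falling in infused patients:

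| Events | Whole arm, n = 217 | Infused only, n = 184 |
|---|---|---|
| 0 | upper limit 1.7% | upper limit 2.0% |
| 2 | 0.9% (0.1 to 3.3) | 1.1% (0.1 to 3.9) |

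The zero-event upper limit is 1 − 0.025^(1/n). It is 2.3% on 158 and 1.9% on 195. For VENUS alone, 0.85 × 180 = 153 are infused, and the limit is 2.0% on 180 against 2.4% on 153. The group attempted without ethanol is small: 0/33 gives an upper limit of 10.6% (6.1% on 59, 15.4% on 22).

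**Crossover infusions.** Two readings are open.

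- *By the section 6.0 C fields:* the acute field names the Day 0 procedure, and the others are tied to the Day 7 and Day 30 contacts. Crossover comes after two in-study procedures, the second for recurrence beyond 3 months, so its complications fall outside both complication endpoints.
- *By the wording of section 5.2 and the stopping rule:* neither names Day 0. The rule's definition is "Procedural adverse events include those that occur within 24 hours of the procedure or those that may be delayed but procedure-related". Crossover complications then count, under the grouping rule, in the PVAI arm.

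On the first reading the dilution factor stays at f. On the second it becomes f − c, where c is the share of the PVAI arm infused and each infusion carries the same excess. The documents give no crossover count. Purely as assumptions, c of 2%, 5% or 10% gives 0.83, 0.80 or 0.75.

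**The case against.** The strongest reply is that the grouping sentence concerns PVAI crossovers and says nothing about failed cannulation. Since 0.85 × 180 = 153 is close to 156, the allocation could be read as aiming for about equal treated groups. If only treated patients were analysed, the factor would be 1. This stands to the extent that 0.85 is conditional. Against it, no sentence removes uncannulated patients, and section 7.6 analyses by treatment group.

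A second reply is that monitoring already covers ethanol harm. Section 7.8.1 captures adverse events related to ethanol ablation through the final visit. Section 7.8.2 holds the study for an unexpected serious event related to the VOM procedure. Section 7.8.3 gives the DSMB unblinded reports so that VOM-attributable events can be identified. None of these excludes crossovers. A reader might infer that crossover ethanol events are recognised nowhere, and these sections show otherwise. What they provide is case-level attribution. They commit to no rate with exposed patients as the denominator.

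A third reply is that the effect is small, that crossovers are probably few given what must come first, and that the exposed rate can be produced from collected data without being planned. The small size is accepted and sets the grade. Planning the table now still avoids choosing exposure groups after events are seen.

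**Conclusion.** The point holds as a minor one. Applied to safety, the grouping rule leaves the planned endpoint analyses without a rate in patients who received ethanol, and it either drops crossover ethanol complications or counts them in the PVAI arm.

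The 0.85 factor (0.73 to 0.90) rests on two assumptions: uncannulated patients stay in the VOM-PV arm, and the harm is confined to infused patients. In absolute terms it moves a zero-event upper limit from 1.7% to 2.0%. No formal safety test, margin or efficacy conclusion depends on it, and the size of the crossover part is unknown.

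A reader might also infer that the 30-day window hides late ethanol harm, such as the pilot's 6-week effusion. The documents do not support adding that here. The window applies equally to both arms, section 7.8 calls the role of ethanol in those effusions unclear, and the stopping rule expressly includes delayed pericardial effusion.

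**What to change.** Keep the randomised comparison and make three additions.

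- In section 6.0 C, add one descriptive safety table by treatment received at the index procedure: ethanol delivered; VOM attempted without ethanol; PVAI only. Give exact confidence intervals for acute complications, 30-day complications and mortality.
- List events after crossover ethanol separately, timed from the infusion.
- In item 5 of sections 5.7 and 5.8, state that the grouping rule does not preclude this table or listing.

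The cost is some wording, one table and one listing. The data are already collected: cannulation success and VOM complications (section 4.2), millilitres used (7.5), additional procedures (5.7 and 5.8 item 4) and adverse events to the final visit (7.8.1). Sample size, alpha, randomisation and visits do not change. The drawback is that the exposure groups are not randomised and the attempted-without-ethanol group is small, so the table can only supplement the comparison by arm.

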5.8 MARS: DEFINITIONS OF PROCEDURAL SUCCESS OR FAILURE AND INDICATIONS FOR REPEAT PROCEDURES

1. **Success:** Freedom from AT/AF clinical recurrence on follow-up visits AND less than 30 seconds of AT/AF on a 1 month continuous electrocardiographic monitor .
2. **Clinical Success.** Freedom from AT/AF clinical recurrence on follow-up visits but documented AF or flutter up to 25% of the time on a 1-month continuous electrocardiographic monitor. The rationale is to account for patients in whom a repeat procedure would not be clinically indicated, yet AF/AT would not be considered cured.
3. **Repeat procedures. A repeat procedure will constitute an effectiveness failure for the purpose of the primary efficacy endpoint.** However, repeat procedures and their outcomes will be recorded for secondary outcome analysis. First, repeat procedures are a clinical reality in persistent AF, and a single-procedure success endpoint –does not capture it. Second, it is possible that VOM-PV on a first procedure may increase success of a second procedure –e. g. if the recurrences in VOM-PV group are as AT instead of AF. Both represent a clinical failure of the procedure, but a repeat procedure for AT is more likely to succeed.⁶⁵ Repeat procedures will be encouraged to be timed within the first 6 months of the randomization procedure. Although this may seem short, it is our clinical experience that the bulk of AF recurrences tend to occur shortly after the blanking period.¹¹⁵ Thus, we expect a minority of patients to recur late in this window.

Indications for a repeat procedure include:

- a. Procedure failure: Symptomatic, recurrent persistent AF or flutter detected clinically during the scheduled follow-up visits.
- b. Less than partial/clinical success: AF or flutter burden on electrocardiographic monitoring exceeding 25% regardless of symptoms. Monitoring will be performed at 6 months post randomization procedure.
- c. Symptomatic AF or flutter detected on electrocardiographic monitoring regardless of AF or flutter burden. Monitoring will be performed at 6 months post randomization procedure.

Data to be collected during a repeat procedure will include

- a. Documentation of PV isolation: number and location of reconnected PV at the baseline of the repeat procedure.
- b. Perimetal conduction: presence or absence of perimetal block.
- c. Mechanisms of atrial flutter, if present.
- d. Documentation of other RF ablation sites
- e. Documentation of RF time, time to perimetal block (if not already achieved), fluoroscopy time, LA instrumentation time, and procedure time.
- f. Baseline and Final LA voltage map (using any commercially available electroanatomical mapping systems). Measurement of baseline and Final LA scar surface area.

4. Effectiveness (Treatment) Failures

Effectiveness failures towards the primary endpoint will include the following (see Figure 8):

- e. Clinical recurrence of AF or AT after 3-months.
- f. Documented AF or AT of 30 seconds or more on EKG monitor at obtained at 6 and 12 months.
- g. Requirement of a repeat ablation procedure for recurrent AT-AF.
- h. Death.

Patients who have a recurrence after 3 months post randomization will have a repeat procedure (PVAI). Patients will be deemed to be effectiveness failure for the primary endpoint of the trial after repeat procedures. Still, subjects will:

- e. Remain in the study for the purpose of all secondary endpoints: these include quality of life, AF burden on event monitoring, success after multiple procedures.
- f. Undergo all clinically necessary procedures and treatments, including prescription of antiarrhythmic therapy and additional procedures needed to control atrial fibrillation or flutter. A crossover VOM procedure will be offered to those randomized to PVAI after 2 in-study procedures.
- g. Data on such additional procedures or treatment will be collected in the Electronic Data Capture system (EDC).
- h. An additional secondary endpoint will be created: total number of procedures performed and requirement of antiarrhythmic drugs.

5. Cross-over option for of patients initially randomized to PVAI only.

If a patient is originally randomized to conventional PVAI and experiences a treatment failure after a repeat procedure he or she may undergo an additional conventional PVAI ablation procedure during the study. Crossover to VOM ethanol will only be allowed after 2 procedures are performed in the setting of study participation. This is allowed because certain recurrent flutters are particularly suited to respond to VOM ethanol. The primary and secondary endpoints will be computed following their original randomization group.

